6.4.6. Tipping Point Analyses

To investigate the missing data mechanism, additional analyses using multiple imputation (MI) under the missing not at random assumption will be provided for the following primary and key secondary objectives:

- EASI75 at Week 16, baricitinib 2-mg compared to placebo
- IGA (0,1) with ≥ 2 -point improvement at Week 16, baricitinib 2-mg compared to placebo
- Itch NRS 4-point improvement from baseline to Week 16, baricitinib 2-mg compared to placebo

All patients in the ITT population will be included in the analyses. Data after the occurrence of intercurrent events (after application of the primary censoring rule) will be set to missing.

Within each analysis, a most extreme case will be considered, in which all missing data for patients randomized to baricitinib 1-mg or 2-mg will be imputed using the worst possible result, and all missing data for patients randomized to placebo will be imputed with the best possible result. Treatment differences will be analyzed using logistic regression (Section 6.2.4).

For continuous variables, the following process will be used to determine the tipping point:

1. To handle intermittent missing visit data, a Markov chain Monte Carlo (MCMC) method (SAS® Proc MI with MCMC option) will be used to create a monotone missing pattern.
2. A set of Bayesian regressions (using SAS® Proc MI with MONOTONE option) will be used for the imputation of monotone dropouts. Starting from the first visit with at least 1 missing value, the regression models will be fit sequentially with treatment as a fixed effect and values from the previous visits as covariates.
3. A delta score is added to all imputed scores at the primary time point for patients in the baricitinib treatment groups, thus worsening the imputed value. The delta score is capped for patients based on the range of the outcome measure being analyzed.
4. Treatment differences between baricitinib and placebo are analyzed for each imputed dataset using ANCOVA (Section 6.2.4). Results across the imputed datasets are aggregated using SAS® Proc MI ANALYZE in order to compute a p-value for the treatment comparisons for the given delta value.
5. Steps 3 and 4 are repeated, and the delta value added to the imputed baricitinib scores is gradually increased. The tipping point is identified as the delta value which leads to a

loss of statistical significance (aggregated p-value >0.05) when evaluating baricitinib relative to the placebo group.

As a reference, for each delta value used in Steps 3 through 5, a fixed selection of delta values (ranging from slightly negative to slightly positive) will be added to imputed values in the placebo group, and Step 4 will be performed for the combination. This will result in a 2-dimensional table, with the columns representing the delta values added to the imputed placebo responses, and the rows representing the delta values added to the imputed baricitinib responses. Separate 2-dimensional tables will compare each baricitinib dose group to placebo.

A similar process will be used for the categorical variables:

1. Missing responses in the baricitinib groups will be imputed with a range of low response probabilities, including probabilities of 0, 0.05, ... 0.3, as appropriate for the data.
2. For missing responses in the placebo group, a range of responses probabilities (eg, probability = 0, 0.05 ... 0.3 by incremental 0.05, increments may be changed after unblinding to best reflect reasonable response rates, as appropriate for the data) will be used to impute the missing values. Multiple imputed datasets will be generated for each response probability.
3. Treatment differences between baricitinib and placebo are analyzed for each imputed dataset using logistic regression (Section 6.2.4). Results across the imputed datasets are aggregated using SAS® Proc MIANALYZE in order to compute a p-value for the treatment comparisons for the given response probability. If the probability values do not allow for any variation between the multiple imputed datasets (eg, all missing responses in the placebo and baricitinib groups are imputed as responders and non-responders, respectively), then the p-value from the single imputed dataset will be used.

The tipping point is identified as the response probability value within the placebo group that leads to a loss of statistical significance when evaluating baricitinib relative to placebo.

For tipping point analyses, the number of imputed data sets will be $m=100$. The seed values to start the pseudorandom number generator of SAS Proc MI (same values for MCMC option and for MONOTONE option) are given in [Table JAIW.6.3](#).

Table JAIW.6.3. Seed Values for Imputation

Analysis	Seed Value
Proportion of patients achieving IGA (0,1) with ≥ 2 -point improvement at Week 16, using primary censoring rule	123470
Proportion of patients achieving EASI75 at Week 16; using primary censoring rule	123471
Proportions of patients achieving a 4-point improvement from baseline in Itch NRS at Week 16, using primary censoring rule	123472

Abbreviations: EASI = Eczema Area and Severity Index score; IGA = Investigator's Global Assessment for atopic dermatitis; NRS = Numeric Rating Scale.

6.5. Multicenter Studies

This study will be conducted by multiple investigators at multiple sites in the US and Canada. Country differences will be assessed in the subgroup analysis as discussed in Section 6.15.

6.6. Multiple Comparisons/Multiplicity

The primary and key secondary endpoints will be adjusted for multiplicity in order to control the overall family-wise Type I error rate at a 2-sided alpha level of 0.05.

The following is a list of primary and key secondary endpoints to be tested. The subscript for H denotes dose (2-mg, 1-mg), the numerical identifier of the endpoint within the dose, and the type of hypothesis (0 for null, 1 for alternative), respectively.

Primary Null Hypotheses:

- $H_{2,1,0}$: Proportion of baricitinib 2-mg patients achieving EASI75 is less than or equal to the proportion of placebo patients achieving EASI75 at Week 16

Key Secondary Null Hypotheses:

- $H_{2,2,0}$: Mean percent change from baseline in EASI score for baricitinib 2-mg patients is less than or equal to the percent change from baseline in EASI score for placebo patients at Week 16
- $H_{2,3,0}$: Proportion of baricitinib 2-mg patients achieving a 4-point improvement in Itch NRS is less than or equal to the proportion of placebo patients achieving a 4-point improvement in Itch NRS at Week 16
- $H_{2,4,0}$: Mean change from baseline in Skin Pain NRS for baricitinib 2-mg patients is less than or equal to the mean change from baseline in Skin Pain NRS for placebo patients at Week 16
- $H_{2,5,0}$: Proportion of baricitinib 2-mg patients achieving a 4-point improvement in Itch NRS is less than or equal to the proportion of placebo patients achieving a 4-point improvement in Itch NRS at Week 4
- $H_{2,6,0}$: Proportion of baricitinib 2-mg patients achieving IGA of 0 or 1 with a ≥ 2 -point improvement from baseline at Week 16 is less than or equal to the proportion of placebo patients achieving IGA of 0 or 1 with a ≥ 2 -point improvement from baseline at Week 16 [IGA0-1]
- $H_{2,7,0}$: Proportion of baricitinib 2-mg patients achieving a 4-point improvement in Itch NRS is less than or equal to the proportion of placebo patients achieving a 4-point improvement in Itch NRS at Week 2
- $H_{2,8,0}$: Proportion of baricitinib 2-mg patients achieving a 4-point improvement in Itch NRS is less than or equal to the proportion of placebo patients achieving a 4-point improvement in Itch NRS at Week 1
- $H_{2,9,0}$: Mean change from baseline in the score of Item 2 of the ADSS for baricitinib 2-mg patients is less than or equal to the mean change from baseline in the score of Item 2 of the ADSS for placebo patients at Week 16

- **H_{2,10,0}:** Mean change from baseline in the score of Item 2 of the ADSS for baricitinib 2-mg patients is less than or equal to the mean change from baseline in the score of Item 2 of the ADSS for placebo patients at Week 1
- **H_{2,11,0}:** Proportion of baricitinib 2-mg patients achieving EASI90 is less than or equal to the proportion of placebo patients achieving EASI90 at Week 16
- **H_{2,12,0}:** Proportion of baricitinib 2-mg patients achieving SCORAD75 is less than or equal to the proportion of placebo patients achieving SCORAD75 at Week 16
- **H_{1,1,0}:** Proportion of baricitinib 1-mg patients achieving EASI75 is less than or equal to the proportion of placebo patients achieving EASI75 at Week 16
- **H_{1,2,0}:** Percent change from baseline in EASI score for baricitinib 1-mg patients is less than or equal to the percent change from baseline in EASI score for placebo patients at Week 16
- **H_{1,3,0}:** Proportion of baricitinib 1-mg patients achieving a 4-point improvement in Itch NRS is less than or equal to the proportion of placebo patients achieving a 4-point improvement in Itch NRS at Week 16
- **H_{1,4,0}:** Mean change from baseline in Skin Pain NRS for baricitinib 1-mg patients is less than or equal to the mean change from baseline in Skin Pain NRS for placebo patients at Week 16
- **H_{1,5,0}:** Proportion of baricitinib 1-mg patients achieving a 4-point improvement in Itch NRS is less than or equal to the proportion of placebo patients achieving a 4-point improvement in Itch NRS at Week 4
- **H_{1,6,0}:** Proportion of baricitinib 1-mg patients achieving IGA of 0 or 1 with a ≥ 2 -point improvement from baseline at Week 16 is less than or equal to the proportion of placebo patients achieving IGA of 0 or 1 with a ≥ 2 -point improvement from baseline at Week 16
- **H_{1,7,0}:** Proportion of baricitinib 1-mg patients achieving a 4-point improvement in Itch NRS is less than or equal to the proportion of placebo patients achieving a 4-point improvement in Itch NRS at Week 2
- **H_{1,8,0}:** Proportion of baricitinib 1-mg patients achieving a 4-point improvement in Itch NRS is less than or equal to the proportion of placebo patients achieving a 4-point improvement in Itch NRS at Week 1
- **H_{1,9,0}:** Mean change from baseline in the score of Item 2 of the ADSS for baricitinib 1-mg patients is less than or equal to the mean change from baseline in the score of Item 2 of the ADSS for placebo patients at Week 16
- **H_{1,10,0}:** Mean change from baseline in the score of Item 2 of the ADSS for baricitinib 1-mg patients is less than or equal to the mean change from baseline in the score of Item 2 of the ADSS for placebo patients at Week 1
- **H_{1,11,0}:** Proportion of baricitinib 1-mg patients achieving EASI90 is less than or equal to the proportion of placebo patients achieving EASI90 at Week 16
- **H_{1,12,0}:** Proportion of baricitinib 1-mg patients achieving SCORAD75 is less than or equal to the proportion of placebo patients achieving SCORAD75 at Week 16

The primary null hypothesis includes testing whether the baricitinib 2-mg is superior to placebo at the primary endpoint, defined as the proportion of placebo patients achieving EASI75 at Week 16. The graphical multiple testing procedure described in Bretz et al. (2011), which is a

closed testing procedure will be used; hence, it strongly controls the family-wise error rate across all endpoints (Alosh et al. 2014).

Figure JAIW.6.1 depicts the graphical testing scheme (including testing order, interrelationships, Type I error allocation, and the associated propagation).

[figure not shown]

Figure JAIW.6.1. Illustration of graphical multiple testing procedure with initial α allocation and weights.

If $H_{2,1,0}$ is not rejected, no further testing is conducted as the α for that test is considered “spent” and cannot be passed to other endpoints. If $H_{2,1,0}$ is rejected, then α will be propagated to $H_{2,2,0}$. The testing process continues with α propagated according to the weights on the corresponding edges displayed in Figure JAIW.6.1, as long as each hypothesis in the sequence can be rejected at its allocated α level. Each time a hypothesis is rejected, the graph is updated to reflect the reallocation of α , which is considered “recycled” by Alosh et al. (2014). This iterative process of updating the graph and reallocating α is repeated until all hypotheses have been tested or when no remaining hypotheses can be rejected at their corresponding α levels.

6.7. Patient Disposition

An overview of patient populations will be summarized by treatment group. Frequency counts and percentages of patients excluded prior to randomization by primary reason for exclusion will be provided for patients who failed to meet study entry requirements during screening.

Patient disposition will be summarized using the ITT population. Frequency counts and percentages of patients will be summarized by treatment group by the following dispositions:

- completed at least the Week 16
- completed the Week 104
- discontinued early from the study
- enrolled in Study JAIX after discontinuation
- rescued
- non-rescued
- reason for discontinuation

A listing of patient disposition will be provided for all randomized patients, with treatment assignment, the extent of their participation in the study, and the reason for discontinuation.

For the Final DBL, patient disposition will be summarized for the Week 16 Responders population, with the disposition status after Week 16.

6.8. Patient Characteristics

Patient characteristics, including demographics and baseline characteristics, will be summarized descriptively by treatment group for the ITT population and for the Week 16 Responders population. Historical illnesses and preexisting conditions will be summarized descriptively by treatment group for the ITT population. No formal statistical comparisons will be made among treatment groups unless otherwise stated.

6.8.1. Demographics

Patient demographics will be summarized as described above. The following demographic information will be included:

- age
- age group (<65 versus ≥ 65)
- age group (<65, ≥ 65 to <75, ≥ 75 to <85, ≥ 85)
- gender (male, female)
- race (American Indian or Alaska Native, Asian, Black or African American, Native Hawaiian or Other Pacific Islander, White, Multiple)
- country
- weight (kg)
- weight category (<60 kg, ≥ 60 to <100 kg, ≥ 100 kg)
- height (cm)
- body mass index (kg/m^2)
- body mass index category (<25 kg/m^2 , ≥ 25 to <30 kg/m^2 , ≥ 30 kg/m^2)

A listing of patient demographics will also be provided for the ITT population.

6.8.2. Baseline Disease Characteristics

The below baseline disease information (although not inclusive) will be categorized and presented for baseline AD clinical characteristics, baseline health outcome measures, and other baseline demographic and disease characteristics as described above:

- duration since AD diagnosis (years)
- duration since AD diagnosis category (0 to <2 years, 2 to <5 years, 5 to <10 years, 10 to <20 years, ≥20 years)
- age at diagnosis (years)
- age group at diagnosis (<18 years, ≥18 to <50 years, ≥50 years)
- habits (Alcohol: Never, Current, Former; Tobacco: Never, Current, Former)
- skin infections treated with a pharmacological agent within past year (yes, no, unknown; number if yes)
- atopic dermatitis flares within past year (yes, no, unknown; number if yes)
- validated IGA for AD score
- Eczema Area and Severity Index (EASI) score
- SCORing Atopic Dermatitis (SCORAD)
- Body Surface Area affected by AD
- Hospital Anxiety Depression Scale (HADS) subscales
- Patient-Oriented Eczema Measure (POEM)
- Itch NRS
- Atopic Dermatitis Sleep Scale (ADSS) Item 2
- Dermatology Life Quality Index (DLQI)
- Skin Pain NRS
- Patient Global Impression of Severity (PGI-S-AD)
- prior therapy (topical therapy only, systemic therapy)
- prior use of Cyclosporine (yes, no)
- Cyclosporine inadequate response (yes, no)
- Cyclosporine intolerance (yes, no)
- Cyclosporine contraindication [ineligible] (yes, no)
- Cyclosporine inadvisable (yes, no)
- prior use of topical calcineurin inhibitors (yes, no)
- topical calcineurin inhibitor inadequate response (yes, no)
- topical calcineurin inhibitor intolerance (yes, no)
- topical calcineurin inhibitor contraindication [ineligible] (yes, no)
- topical calcineurin inhibitor inadvisable (yes, no)
- vaccine:
 - zoster vaccine (Yes, No)
 - tuberculosis (TB) vaccine (Yes, No)
- baseline renal function status: impaired (estimated glomerular filtration rate [eGFR] <60 mL/min/1.73 m²) or not impaired (eGFR ≥60 mL/min/1.73 m²)
- immunoglobulin E (IgE): intrinsic(<200 kU/I) or extrinsic (≥200 kU/I)

6.8.3. *Historical Illness and Preexisting Conditions*

Historical illnesses are defined as those conditions recorded in the Preexisting Conditions and Medical History electronic case report form (eCRF) or from the Prespecified Medical History: Comorbidities eCRF with an end date prior to the informed consent date. The number and percentage of patients with selected historical diagnoses will be summarized by treatment group using the ITT population. Historical diagnoses will be categorized using the Medical Dictionary for Regulatory Activities (MedDRA; most current available version) algorithmic Standardized MedDRA Queries (SMQs) or similar pre-defined lists of Preferred Terms (PTs) of interest.

Preexisting conditions are defined as those conditions recorded in the Preexisting Conditions and Medical History eCRF, or the Prespecified Medical History: Comorbidities eCRF with a start date and time prior to the informed consent and with a stop date that is after the informed consent date or have no stop date (ongoing). Adverse events are recorded in the eCRFs. For events recorded on AE page, we considered it as a preexisting event if it's onset date was before first dose date. For events occurring on the day of the first dose of study treatment, the date and time of the onset of the event will both be used to determine if the event was preexisting. Conditions with a partial or missing start date (or time if needed) will be assumed to be 'not preexisting' unless there is evidence, through comparison of partial dates, to suggest otherwise. Preexisting conditions will be categorized using the SMQs or similar pre-defined lists of PTs of interest. Frequency counts and percentages of patients with selected preexisting conditions will be summarized by treatment group using the ITT population.

6.9. **Treatment Compliance**

Patient compliance with study medication will be assessed at each visit using the ITT population. For the Final DBL, compliance will be summarized for the Week 16 Responders population.

All patients are expected to take 2 tablets daily as described in the protocol. A patient is considered noncompliant if he or she misses >20% of the prescribed doses during the study, unless the patient's study drug is withheld by the investigator. For patients who had their treatment temporarily interrupted by the investigator, the period of time the dose was withheld will be appropriately adjusted in the 'expected number of total tablets' element of the compliance calculation given below.

Compliance in the period of interest up to Visit x will be calculated as follows:

$$\text{Compliance} = 100 * \frac{\text{total number of tablets dispensed} - \text{total number of tablets returned}}{\text{expected number of total tablets}}$$

where

- Total number of tablets dispensed: sum of tablets dispensed in the period of interest prior to Visit x ;
- Total number of tablets returned: sum of the tablets returned in the period of interest prior to and including Visit x ;
- Expected number of tablets: number of days in the period of interest*number of tablets taken per day = [(date of visit – date of first dose + 1) – number of days of temporary drug interruption]*number of tablets taken per day

Patients who are significantly noncompliant (compliance <80%) through Week 16 will be excluded from the PPS population.

Descriptive statistics for percent compliance and non-compliance rates will be summarized for the ITT population by treatment group for Week 0 through Week 16. For the Final DBL, compliance will be summarized for Week 16 Responders by treatment group for Week 16 through Week 104. Sub-intervals of interest, such as compliance between visits, may also be presented. The number of expected doses, tablets dispensed, tablets returned, and percent compliance will be listed by patient for Week 0 through Week 16 and through Week 104.

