6.14.2. Adverse Events

Adverse events are recorded in the eCRFs. Each AE will be coded to System Organ Class (SOC) and preferred term (PT) using the Medical Dictionary for Regulatory Activities (MedDRA) version that is current at the time of database lock. Severity of AEs is recorded as mild, moderate, or severe.

A TEAE is defined as an event that either first occurred or worsened in severity after the first dose of study treatment and on or prior to the last visit date during the analysis period. The analysis period is defined as the treatment period plus up to 30 days off-drug follow-up time.

A TEAE defined for the final DBL (Week 16 to end of study) is defined as an event that either first occurred or worsened in severity after the Week 16 visit date and on or prior to the last visit date during the analysis period. The analysis period is defined as the treatment period from the Week 16 visit date plus up to 30 days off-drug follow-up time. The baseline severity is defined as the most severity in the baseline period that is between the first dose date and the Week 16 visit date.

Adverse events are classified based upon the MedDRA PT. The MedDRA Lowest Level Term (LLT) will be used in defining which events are treatment-emergent. The maximum severity for each LLT during the baseline period up to first dose of the study medication will be used as baseline. If an event with missing severity is preexisting during the baseline period, and persists during the treatment period, then the baseline severity will be considered mild for determining treatment emergence (ie, the event is treatment-emergent if the severity is coded moderate or severe postbaseline and not treatment-emergent if the severity is coded mild postbaseline). If an event occurring postbaseline has a missing severity rating, then the event is considered treatment-emergent, unless the baseline rating is severe, in which case the event is not treatment-emergent. The day and time for events where onset is on the day of the first dose of study

treatment will both be used to distinguish between pretreatment and posttreatment in order to derive treatment emergence. Should there be insufficient data for AE start date to make this comparison (eg, the AE start year is the same as the treatment start year, but the AE start month and day are missing), the AE will be considered treatment-emergent.

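### Section 6.9 counts expected tablets from first dose, so compliance for Week 16 to 104 at the final lock is understated as written

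*SAP*

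**What the plan says.** Section 6.9 defines compliance as 100 times tablets dispensed minus tablets returned, divided by expected tablets, at 2 tablets daily. Dispensed tablets are the "sum of tablets dispensed in the period of interest prior to Visit" x, and returned tablets are limited to the same period. Expected tablets are "number of days in the period of interest*number of tablets taken per day = [(date of visit – date of first dose + 1"), less days of temporary interruption, times tablets per day.

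The section applies this to more than one period:
- Week 0 to 16 in the ITT population. This feeds the per-protocol set: "Patients who are significantly noncompliant (compliance <80%) through Week 16 will be excluded from the PPS population".
- The final lock: "For the Final DBL, compliance will be summarized for Week 16 Responders by treatment group for Week 16 through Week 104".
- Optional shorter periods: "Sub-intervals of interest, such as compliance between visits, may also be presented".

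No other start date is given. Section 3 records that Version 4 added the final-lock summary to Section 6.9.

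Section 6.14.2 raises a related scoping matter. Its paragraph for the final lock says that "baseline severity is defined as the most severity in the baseline period that is between the first dose date and the Week 16 visit" date. The next paragraph names no lock and says: "The maximum severity for each LLT during the baseline period up to first dose of the study medication will be used as baseline". Its rules for onset on the first-dose day and for incomplete start dates also refer to the start of treatment.

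**The concern.** The numerator covers the period of interest. The denominator, as spelled out, always starts at first dose. For Week 16 to 104 the denominator therefore includes about 16 weeks of tablets that the numerator leaves out.

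The resulting error depends on how long the patient stays. Section 5 requires patients whose IGA returns to 3 or more after Week 16 to leave the study, so follow-up after Week 16 will vary. Early leavers would score low for a reason unrelated to tablet intake. If the arms differ in time to leaving, the by-arm table could show a compliance difference that is only an artefact.

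**Working it through.** The SAP states no compliance figure to reproduce, so the check applies the formula to a simple case.

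**Inputs.** From Section 6.9: 2 tablets a day, and the numerator restricted to the period. Illustrative assumptions: the Week w visit falls 7w days after first dose, there are no interruptions, and every tablet is taken.

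**Week 0 to 16, where the formula fits.** Tablets taken: 2 × 112 = 224. Expected: 2 × (112 + 1) = 226. Compliance: 224/226 = 99.1%. The small shortfall comes from the added day.

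**Week 16 to visit w, as written.** Taken: 2 × 7(w − 16). Expected: 2 × (7w + 1).

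| Visit week | Taken | Expected as written | Score as written | Expected from Week 16 visit, no added day |
|---|---|---|---|---|
| 28 | 168 | 394 | 42.6% | 168 |
| 40 | 336 | 562 | 59.8% | 336 |
| 52 | 504 | 730 | 69.0% | 504 |
| 64 | 672 | 898 | 74.8% | 672 |
| 76 | 840 | 1066 | 78.8% | 840 |
| 88 | 1008 | 1234 | 81.7% | 1008 |
| 104 | 1232 | 1458 | 84.5% | 1232 |

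With the last column as denominator, every score is 100%.

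**Partial intake.** A patient who truly takes 80% after Week 16 scores 0.8 times the written figure: 34.1% at Week 28, 55.2% at Week 52 and 67.6% at Week 104.

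**Between visits, as written.** Week 12 to 16: 56/226 = 24.8%. Week 88 to 104: 224/1458 = 15.4%. Both should be 100%.

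**Two details of the repair.**
- Keeping the added day when a period starts at a visit counts the boundary day in two adjacent intervals. Full intake then gives 56/58 = 96.6% for Week 12 to 16, and 14/16 = 87.5% for Week 1 to 2.
- Interruption days must be limited to the period. Suppose the start moves to Week 16 but an illustrative 28-day interruption before Week 16 is still subtracted. Full intake to Week 52 (252 days) then gives 504/(2 × (252 − 28)) = 504/448 = 112.5%.

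**Can first dose mean the first dose in the period?** Section 6.14.1 counts exposure from the first dose of study drug and starts the final-lock exposure ranges at 112 days. The final-lock rule in Section 6.14.2 treats the first dose date and the Week 16 visit date as different dates. At the final lock, first dose therefore still means Week 0.

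**The case against.** **The intent is plain.** All three elements are tied to the period of interest, and the expansion looks like a leftover from the Week 0 to 16 formula. A careful programmer might follow the defining phrase and ignore the expansion. This is fair, and it is why the point is minor. The written equation is still wrong for two of its stated uses, and no other start date is supplied. The expansion does fit a per-patient listing through Week 104 if that listing runs from Week 0.

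**The 80% cut-off.** A full-intake patient's written score reaches 80% only when (d − 112)/(d + 1) ≥ 0.8, that is at d = 564 days or about Week 80.6. A reader might infer that fully adherent patients will be labelled noncompliant until then. The SAP does not support that. It names noncompliance rates and the below-80% exclusion only for Week 0 to 16. The other rule, "A patient is considered noncompliant if he or she misses >20% of the prescribed doses during the study", runs over the whole study, so it gives no Week 16 to 104 verdict either. A patient who missed half the tablets before Week 16 (112 of 224) and none afterwards has missed 112 of 392, or 28.6%, by Week 28.

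**Adverse events.** A reader might infer that the final-lock count of treatment-emergent events depends on which baseline is programmed. It should not, because the paragraph labelled for the final lock sets its own onset anchor, analysis period and baseline severity, and a specific rule displaces a general one. A reader might also fear that an event dated only with the year of treatment start is counted when Week 16 falls in the next year. The incomplete-date rule applies only when the data are insufficient to make the comparison. In that case the year alone places the event before Week 16, so it is already excluded. What is missing is Week 16 wording for onset on the visit day and for years that leave the order unclear.

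**Conclusion.** The point holds for the compliance formula, at minor severity. As written, Week 16 to 104 compliance for a patient who misses nothing is understated by about 57 percentage points at Week 28 (100 − 42.6), 31 at Week 52 (100 − 69.0) and 15 at Week 104 (100 − 84.5). Between-visit figures after the first interval are also too low.

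The sizes assume nominal visit dates, no interruptions, and a literal reading of the expansion alongside a numerator limited to the period. The possible artefact between arms is an inference; the SAP gives no figures on time to leaving.

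The reach is limited to descriptive output in Week 16 Responders and to optional between-visit summaries. Week 0 to 16 compliance, the per-protocol set, and the primary and key secondary results do not change. Section 6.14.2 needs editorial labelling only, and its effect cannot be sized because the SAP gives no event rates.

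**What to change.** In Section 6.9:
- Replace the first-dose date in the expansion with the start date of the period of interest: first dose for Week 0 to 16, the Week 16 visit for the final lock, and the interval start for between-visit summaries.
- Subtract only interruption days that fall within that period.
- Drop the added day where the period starts at a visit.
- State whether the listing through Week 104 runs from Week 0 or from Week 16.

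In Section 6.14.2, as an editorial note, label the first-dose rules for baseline severity, onset day and incomplete dates as applying to the locks before the final one. Give Week 16 counterparts for the final lock and leave its existing baseline definition as it is.

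The cost is a few phrases and a small change to the compliance program. No new data are needed, and no Week 16 result has to be rerun.
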